### 9.4.2 Identity of Investigational Products

### 9.4.2.1 Pegloticase

[figure not shown]
Pegloticase is a clear, colorless, sterile solution in phosphate-buffered saline intended for IV infusion after dilution. Each mL of pegloticase contains 8 mg of uricase protein conjugated to 24 mg of 10 kDa monomethoxypoly (ethylene glycol). Excipients include disodium hydrogen phosphate dihydrate, sodium chloride, sodium dihydrogen phosphate dihydrate, and water for injection.

#### 9.4.2.2 Methotrexate

MTX 2.5 mg tablets for oral administration will be provided to subjects as a commercially available generic (MTX Full Prescribing Information).

A dosing calendar will be provided to subjects at the Week -4 Visit to record each dose of MTX and the date and time of each dose on each calendar day of MTX administration. Additional calendar pages may be provided on future visits as needed.

### 9.4.3 Labeling

be provided to study subjects after the Week -4 Visit for weekly dosing after visit procedures and inclusion/exclusion criteria are confirmed.

### 9.4.4 Storage

Before preparation for use, pegloticase will be stored in the carton, maintained under refrigeration between 2°C and 8°C (36°F and 46°F), protected from light, and will not be shaken or frozen. Pegloticase diluted in infusion bags is stable for 4 hours at 2°C to 8°C (36°F to 46°F) and for 4 hours at room temperature (20°C to 25°C, 68°F to 77°F).

MTX will be stored between 20°C to 25°C (68°F to 77°F) and protected from light.

# 9.4.5 Drug Accountability

Clinical supplies will be dispensed only in accordance with the protocol. Accurate records of the clinical supplies received, the amount dispensed for each subject, and the amount remaining at the conclusion of the study will be maintained. Each study site will also maintain subject drug logs/electronic logs to account for MTX dispensed, and subject compliance will be monitored by the site at each visit (see Section 9.4.9).

Subjects will bring the MTX dosing calendar to each study visit for assessment of compliance. Subjects will bring the MTX bottle to each visit for a compliance check by the site. The site will manually count the pills and re-dispense the bottle to the subject. At the end of the study or if the subject prematurely discontinues the study, the subjects will return any unused or partially used study drugs to the site.

Investigational clinical supplies will be received by a designated person at the study site, handled and stored safely and properly, and kept in a secured location to which only the Investigator and designated assistants have access.

Please reference the Study Pharmacy Manual for more detailed information on MTX and pegloticase packaging, labeling, storage, and destruction.

### 9.4.6 Study Drug Administration and Timing of Dose for each Subject

### 9.4.6.1 Description of Clinical Supplies

will supply study drugs (pegloticase and MTX) to clinical sites. Ancillary supplies for dosing will be provided by the study site (i.e., infusion bags containing normal saline, syringes, needles, alcohol swabs, gauze pads, bandages, and biohazard containers for safe storage of used needles and syringes).

#### 9.4.6.2 Determination of Dose Volume

Pegloticase will be administered as an admixture of 8 mg in 250 mL of 0.45% or 0.9% Sodium Chloride Injection, United States Pharmacopeia (USP) for IV infusion.

In the event of an IR, the infusion should be slowed, or stopped, and restarted at a slower rate at the discretion of the Investigator. Infusions subsequent to an IR in an individual subject may be PRIVATE AND CONFIDENTIAL INFORMATION OF HORIZON THERAPEUTICS IRELAND DAC

Page 55 of 129

given in a larger volume of diluent, not to exceed 500 mL. In this case, the infusion duration will also be extended to a minimum of 3 hours.

### 9.4.6.3 Details Concerning Timing and Dose Administration

# 9.4.6.3.1 Preparation and Administration

### 9.4.6.3.1.1 Preparation

Vials of pegloticase will be visually inspected for particulate matter and discoloration before administration, whenever solution and container permit. Vials will not be used if either is present. Using appropriate aseptic technique, 1 mL of pegloticase will be withdrawn from the vial into a sterile syringe. Any unused portion of product remaining in the vial will be discarded. Syringe contents will be injected into a single 250 mL bag of 0.45% or 0.9% Sodium Chloride Injection, USP for IV infusion and will not be mixed or diluted with other drugs. The infusion bag containing the dilute pegloticase solution will be inverted a number of times to ensure thorough mixing but will not be shaken. In accordance with good pharmacy practice, gloves will be worn during preparation of the dose.

Pegloticase must be started within 4 hours of dilution. Before administration, the diluted solution of pegloticase will be allowed to reach room temperature. Pegloticase must never be subjected to artificial heating.

#### 9.4.6.3.1.2 Dose and Administration

### **Methotrexate**

During the MTX Run-in Period, which begins 4 weeks prior to the first dose of pegloticase, subjects will take oral MTX at a dose of 15 mg weekly. Subjects will be instructed to take MTX once weekly on the same day each week (if dosing more frequently than once in the day (i.e. BID, TID), the total MTX dose should be taken within the same calendar day) and record the date and time of each dose on each calendar day of MTX administration.

During the MTX Run-in Period, if a dose is missed, it should be taken as soon as it is remembered. If it is within 48 hours of the next scheduled dose, the subject will be instructed to skip the missed dose and resume at the next regularly scheduled time; thus, subjects will be instructed not to double a dose to make up for a missed dose if within 48 hours of the next dose. If a dose is missed, or if infusion schedules are adjusted and MTX dose must be moved from the regular day, it is recommended that the doses are at least 5 days apart if possible, however it is safe for MTX doses to be administered with a minimum of 3 days apart.

During the Pegloticase + IMM Period, subjects will be instructed to take MTX 1 to 3 days prior to the dose of pegloticase; however, if a subject does not do so, MTX must be taken ≥60 minutes prior to pegloticase infusion. Subjects will dose Methotrexate weekly until one week after the last infusion.

If a subject becomes unable to tolerate the prescribed dosage of MTX after Day 1 during the Pegloticase + IMM Period, the dosage may be decreased (see Section 9.4.6.3.2.2).

Refer to Section 9.4.11 for contraception requirements.

Subjects will take folic acid 1 mg orally every day beginning at Week -4 (the start of MTX) until prior to the Week 52 Visit or the last infusion visit. Folic acid will be supplied by a local pharmacy.

### **Pegloticase**

All subjects will receive pegloticase at the same dose of 8 mg administered IV every 2 weeks for a total of 26 infusions from Day 1 through Week 50, inclusive (Pegloticase + IMM Period). Subjects will not be fasting on the day of infusion and will be encouraged to have a snack or normal meal before or after the infusion. Pre-infusion sUA results must be reported by the local or central laboratory prior to pegloticase infusion (see Section 9.5.1.1).

Standardized IR prophylaxis consisting of pre-treatment with antihistamines, acetaminophen, and corticosteroids will accompany each infusion (see Section 9.4.1.3). The drug name, dose, and timing of these prophylactic medications will be recorded.

Pegloticase will be administered as an admixture of 8 mg in 250 mL of 0.45% or 0.9% Sodium Chloride Injection, USP for IV infusion by gravity feed or infusion pump. Pegloticase will not be administered as an IV push or bolus.

In a patent IV site, using tubing with no in-line filter, the pegloticase preparation will be infused over approximately  $120 \pm 15$  minutes while the subject is under close observation for any signs of distress. If an in-line filter is used, it should be  $0.2~\mu m$  or larger. At the end of the infusion, the IV line will be flushed with 10~mL of normal saline to ensure the full dose is administered. The date and time of infusion start and stop (inclusive of the IV flush) will be recorded.

### 9.4.6.3.2 Dose Modifications, Interruptions, and Delays

# 9.4.6.3.2.1 Pegloticase Modifications

Administration of pegloticase will be immediately held if the subject experiences any significant IR such as respiratory distress, agitation, chest or back pain, urticaria, or another clinically significant event occurring during infusion. If the AE meets the definition of an SAE for IR, the infusion should not be restarted unless the site Investigator determines it is safe to resume the infusion. If the AE does not meet the definition of an SAE for IR, the site Investigator may make the decision to re-start the infusion depending upon the nature and severity of the AE.

Infusions subsequent to an IR in an individual subject may be given in a larger volume of diluent, not to exceed 500 mL. In this case, the infusion duration will also be extended to a minimum of 3 hours. The total volume and duration of infusion will be captured in the medical record and eCRF.

### 9.4.6.3.2.2 MTX Dose Titration Algorithm and Intolerance Criteria

During the MTX Run-in a subject will be considered a screen failure if any of the following new laboratory findings or symptoms reflecting MTX intolerance occur:

PRIVATE AND CONFIDENTIAL INFORMATION OF HORIZON THERAPEUTICS IRELAND DAC

Page 57 of 129

- 1. Abnormal Hematology findings:
  - a. WBC  $< 3.5 \times 10^9/L$
  - b. Platelets  $< 75 \times 10^9/L$
  - c. Hematocrit < 32%
- 2. Abnormal hepatic function findings:
  - a. AST/ALT >1.5 x upper limit of reference range and
  - b. Albumin < lower limit of reference range
- 3. Abnormal renal function: eGFR <40ml/min/1.73 m^2 (as estimated with the MDRD equation).
- 4. New clinically important signs and symptoms, such as the following:
  - a. Rash or oral ulceration
  - b. Persistent nausea, vomiting and diarrhea
  - c. New or increasing dyspnea or dry cough, or unexplained cough with fever
  - d. Severe sore throat, abnormal bruising
  - e. Severe headaches, fatigue, and problems concentrating

Note that if minor clinical symptoms emerge, such as mild stomatitis, mild GI discomfort, etc., the investigator may increase folic acid dose (e.g. 2 mg daily) or recommend a divided dose of MTX (e.g. 3 tabs of 2.5 mg in the morning and evening on the day of dosing); if symptoms improve, subject will not be considered a screen failure on the basis of that symptom.

During the Run-In and Pegloticase+IMM Period, MTX dose guidance based on new laboratory findings or new symptoms is as follows:

Lab Parameters	Value	MTX Dose Change
WBC	$3.0 \times 10^9/L \sim 3.5 \times 10^9/L$	Decrease to 10 mg
	< 3.0 x 10  /L	Temporary stop
Platelets	< 50 x 10  /L	Temporary stop
Hematocrit	< 27%	Temporary stop
AST/ALT	Between 1.5 ~ 2 x ULN	Decrease to 10 mg
	> 2 x ULN	Temporary stop
eGFR	< 30 ml/min/1.73 m 	Temporary stop
New clinically important symptoms/signs*	Yes	Temporary stop

\* New clinically important symptoms or important medical events:

KRYSTEXXA IND: 010122

- a. Rash or oral ulceration
- b. Persistent nausea, vomiting and diarrhea
- c. New or increasing dyspnea or dry cough, or unexplained cough with fever
- d. Severe sore throat, abnormal bruising
- e. Severe headaches, fatigue, and problems concentrating
- f. Any other important medical events that might increase methotrexate toxicity or pre-dispose to new or worsening infection (e.g. undergoing surgery, hospitalization, being treated with antibiotics, having a clinical infection, developing new clinically significant pericardial / pleural effusion or ascites)

Note that if minor clinical symptoms emerge, such as mild stomatitis, mild GI discomfort, etc., the investigator may increase folic acid dose to 2 mg daily or recommend a divided dose of MTX (e.g. 3 tabs of 2.5 mg in the morning and evening on the day of dosing) and monitor for symptom resolution.

Investigators should discuss the emergence of any one of the following criteria with the medical monitor to review the case:

- 1.  $ALT/AST > 1.5 \times ULN$  on 3 of any 5 consecutive measures
- 2. Albumin < 0.8 x LLN on 2 consecutive measures
- 3. Any laboratory or clinical symptoms leading to temporary stop on 3 consecutive measures, in which case the medical monitor will review to consider re-initiation, a continued temporary stop, or a permanent stop in discussion with the PI.

Guidance for increasing MTX back towards 15 mg after dose reduction, based on improvement or resolution of abnormal liver enzymes (>2 × upper limit of normal):

- 1. When liver enzymes return to values ≤1.5 × upper limit of normal, increase MTX or dose by 2.5 mg and reassess in 2 weeks.
- 2. If liver enzymes remain ≤1.5 × upper limit of normal, increase MTX or dose by 2.5 mg and reassess in 2 weeks.

Improvement of other laboratory abnormalities potentially attributed to MTX or may also warrant titration back up to 15 mg weekly, based on PI judgement and in discussion with the Sponsor medical monitor.

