### 9.3 Selection of Study Population

#### 9.3.1 Inclusion Criteria

Eligible subjects must meet all of the following criteria:

1. Willing and able to give informed consent.

KRYSTEXXA IND: 010122 Protocol: HZNP-KRY-201 Version 3.0, Adminstrative Change 1

2. Willing and able to comply with the prescribed treatment protocol and evaluations for the duration of the study.

- 3. Adult men or women  $\geq$ 18 to  $\leq$ 65 years of age.
- 4. Women of childbearing potential (including those with an onset of menopause <2 years prior to screening, non-therapy-induced amenorrhea for <12 months prior to screening, or not surgically sterile [absence of ovaries and/or uterus]) must have negative serum/urine pregnancy tests during the Screening/MTX Run-in Period; subjects must agree to use 2 reliable forms of contraception during the study, one of which is recommended to be hormonal, such as an oral contraceptive. Hormonal contraception must be started ≥1 full cycle prior to Week -4 (start of MTX dosing) and continue for 30 days after the last dose of pegloticase or at least one ovulatory cycle after the last dose of MTX (whichever is the longest duration after the last dose of pegloticase or MTX). Highly effective contraceptive methods (with a failure rate <1% per year), when used consistently and correctly, include implants, injectables, combined oral contraceptives, some intrauterine devices, sexual abstinence, or vasectomized partner.
- 5. Men who are not vasectomized must not impregnate their female partner during the study and for at least 3 months after the last dose of MTX.
- 6. Hyperuricemia at the Screening, Week -4, or Week -2 Visit of the Screening/MTX Run-in Period, as documented by sUA ≥6 mg/dL.
- 7. Uncontrolled gout, defined as meeting the following criteria:
  - sUA ≥6 mg/dL prior to entry into the Pegloticase + IMM Period (any laboratory tests during screening up to and including during the MTX Run-in Period) and at least 1 of the following:
    - inability to maintain sUA <6 mg/dL on other urate-lowering therapy
    - intolerable side effects associated with current urate-lowering therapy
    - functionally limiting tophaceous deposits (including those detected clinically or by DECT imaging)
- 8. Able to tolerate MTX 15 mg for 4 weeks during the Screening/MTX Run-in Period prior to the first dose of pegloticase.

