#### 9.3.4.3 Screen Failures

Subjects who do not meet all of the inclusion criteria or meet any of the exclusion criteria will be considered screen failures. In addition, subjects who are unable to tolerate MTX at an oral dose of 15 mg weekly during the MTX Run-in Period will be considered screen failures. Screen failure subjects who are females of childbearing potential who took at least one dose of MTX, will receive a Safety Follow-up Phone call/E-mail/Site Visit approximately 30 days after the last dose of MTX to verify at least one ovulatory cycle after the last dose of MTX. If the subject has not ovulated, a urine pregnancy test will be performed at the study site. Screen failure subjects who receive at least 1 dose of MTX and are non-vasectomized males will receive a Phone/E-mail/Site Visit 3 months after MTX discontinuation regarding partner pregnancy.

Screen failure subjects may be allowed to rescreen for the study if both the Investigator and Sponsor are in agreement regarding rescreening and if the Investigator determines that the subject can satisfy all of the eligibility criteria.

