#### 9.4.9 Restricted Medications

Subjects should not receive the following medications from the time of Screening through the end of pegloticase and MTX treatment:

- Oral urate-lowering therapies including allopurinol, febuxostat, probenecid, lesinurad, or other ULT for gout.
- Any PEG-conjugated drug
- Any other investigational agent
- Methotrexate (other than study investigational product), azathioprine, mycophenolate mofetil, or other systemic immunosuppressants aside from glucocorticoids for gout flare prophylaxis (< 10 mg prednisone or equivalent per day) or intermittent gout flare treatment
- If a subject is treated with antibiotics, refer to Section 9.4.6.3.2.2.
- Systemic immunosuppressive agents

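### Section 9.4.6.3.2.2 gives two outcomes for the same MTX Run-in findings: screen failure in its list, a reduced or paused dose in its table

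*Protocol*

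**What the plan says.** The relevant text is in protocol Section 9.4.6.3.2.2, with supporting statements elsewhere.

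- **The list.** In the MTX Run-in, "a subject will be considered a screen failure if any of the following new laboratory findings or symptoms reflecting MTX intolerance occur". It names WBC <3.5 x 10^9/L, platelets <75 x 10^9/L, hematocrit <32%, a hepatic criterion, eGFR <40 mL/min/1.73 m², and clinically important signs and symptoms with examples a to e. The hepatic criterion has two parts: "AST/ALT >1.5 x upper limit of reference range and" albumin below the reference range.
- **The table.** Its heading reads "During the Run-In and Pegloticase+IMM Period, MTX dose guidance based on new laboratory findings or new symptoms is as follows". It cuts MTX to 10 mg for WBC 3.0 to 3.5 or AST/ALT 1.5 to 2 x ULN. It stops MTX temporarily for WBC <3.0, platelets <50, hematocrit <27%, AST/ALT >2 x ULN, eGFR <30, or clinically important symptoms or events. The symptoms are the same a to e, plus item f: "Any other important medical events that might increase methotrexate toxicity or pre-dispose to new or worsening infection".
- **Tolerance of 15 mg.** Inclusion criterion 8 (Section 9.3.1) reads "Able to tolerate MTX 15 mg for 4 weeks during the Screening/MTX Run-in Period". Section 9.3.4.3 makes screen failures of "subjects who are unable to tolerate MTX at an oral dose of 15 mg weekly during the MTX Run-in Period". The Synopsis (Dose Regimen, Pegloticase) likewise gives pegloticase only to subjects who tolerated 15 mg weekly in the Run-in.
- **When the dose may be reduced.** The Synopsis (Dose Regimen, MTX) and Sections 9.1, 9.4.1 and 9.4.6.3.1.2 place dose reduction after Day 1 or in the Pegloticase + IMM Period.
- **Antibiotics.** Section 9.4.9, which applies from Screening onward, says "If a subject is treated with antibiotics, refer to Section 9.4.6.3.2.2".

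**The concern.** Two rules name the same weeks and the same findings but point in different directions. One ends the subject's candidacy. The other keeps the subject on MTX at a lower dose, or pauses it with a view to resuming. A site that follows the list records a screen failure, while a site that follows the table carries the subject toward Day 1.

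What is at stake is consistent handling of possible MTX toxicity and a clear eligibility rule at approximately 8 centers. The decision also determines the analysis population. Under Section 9.6.2, a subject who took MTX is in the ITT population either way, but enters the mITT population only after a dose of pegloticase.

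**Working it through.** No arithmetic applies. The check applies the list and the table to the same Run-in finding and compares the outcomes.

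| Run-in finding | List | Table | Relation |
|---|---|---|---|
| WBC 3.0 to <3.5 | screen failure | cut to 10 mg | direct conflict |
| AST/ALT >1.5 to 2 x ULN, albumin low | screen failure | cut to 10 mg | direct conflict |
| WBC <3.0 | screen failure | temporary stop | tension |
| Platelets <50 | screen failure | temporary stop | tension |
| Hematocrit <27% | screen failure | temporary stop | tension |
| eGFR <30 | screen failure | temporary stop | tension |
| AST/ALT >2 x ULN, albumin low | screen failure | temporary stop | tension |
| Symptoms a to e | screen failure | temporary stop | tension |
| Platelets 50 to <75, hematocrit 27 to <32%, eGFR 30 to <40 | screen failure | no entry | no conflict |
| AST/ALT >1.5 to 2 x ULN, albumin normal | not listed | cut to 10 mg | outcome not stated |
| AST/ALT >2 x ULN, albumin normal | not listed | temporary stop | outcome not stated |
| Item f events that are not signs or symptoms (e.g. surgery, antibiotic treatment) | not listed | temporary stop | outcome not stated |

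**Direct conflict.** A WBC of 3.2 is a screen failure under the list and continued dosing at 10 mg under the table. Both cannot be carried out. For AST/ALT of 1.8 x ULN the same holds only if albumin is also low, because the two parts of the hepatic criterion are joined by *and*.

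**Tension.** Stopping MTX in a subject who is also a screen failure can be done. The difficulty is the word *temporary*: it presumes a subject who stays in the study and may restart.

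**Heading against other sections.** The table heading extends dose guidance to the Run-in. Sections 9.1, 9.4.1 and 9.4.6.3.1.2, which all refer to this section for dose reduction, do so for the time after Day 1 or the Pegloticase + IMM Period.

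**Outcome not stated.** With AST/ALT of 1.8 or 2.5 x ULN and normal albumin, the list is not met, but the table takes the subject off 15 mg. Criterion 8 and Section 9.3.4.3 turn on tolerance of 15 mg. No sentence says whether a reduction or stop directed by the table is a failure of tolerance. The same question arises for surgery or antibiotic treatment under item f, and Section 9.4.9 sends antibiotic use to this section from Screening onward.

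**The case against.** The strongest reply is that the protocol, read as a whole, leans toward screen failure. The list is mandatory and the table is called guidance. Eligibility is checked again at Week -2 and Day 1 (Sections 9.5.6.1.3 and 9.5.6.2.1), and other sections keep dose reduction for later. This stands as an indication of intent, but it does not remove the conflict, because the table heading expressly adds the Run-in.

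A second reply is that the list covers only findings that reflect MTX intolerance, leaving the table for findings with another cause. The text does not draw that line, and it would not help for findings attributed to MTX.

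Several stronger readings are tempting but go further than the document allows:

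- *Every table row flatly contradicts the list.* Most rows say temporary stop, which can be acted on together with a screen failure, and Section 9.3.4.3 permits rescreening. Only the two cuts to 10 mg collide directly, and the AST/ALT one only when albumin is low.
- *Raised AST/ALT with normal albumin falls under no rule at all.* The list does not claim to be exhaustive, and the 15 mg tolerance requirement in the Synopsis and Sections 9.3.1 and 9.3.4.3 applies independently. What is missing is the sentence linking a table-directed cut or stop to that requirement.
- *All of item f escapes the list.* The list's symptom item is open-ended, so events that present as signs or symptoms, such as a clinical infection, may fall within it. Surgery or antibiotic treatment as such does not.
- *A cut at Week -2 could not be reversed by Day 1.* The step-up text ("increase MTX or dose by 2.5 mg and reassess in 2 weeks") is worded for enzymes above 2 x ULN, where the table's action is a temporary stop and not 10 mg. For other abnormalities, re-titration is left to judgement with the medical monitor. No recovery timetable can be derived for a cut to 10 mg.
- *The response rate is biased.* Nothing in the document shows how many subjects would be affected or in which direction.

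**Conclusion.** The contradiction is real and confined to one section. Its firm core is the table heading's reach into the Run-in and the two 10 mg rows: WBC 3.0 to <3.5 regardless of other values, and AST/ALT >1.5 to 2 x ULN with low albumin. The temporary-stop rows add tension. AST/ALT >1.5 x ULN with normal albumin, and item f events that are not signs or symptoms, lack a stated link to the 15 mg tolerance rule.

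The practical window is narrow. After MTX starts, Week -2 is the only scheduled safety laboratory visit before the Day 1 pre-infusion sample (Section 9.5.4.7), although symptoms and medical events can arise at any time. The frequency is unknown and no effect on the response rate is claimed. The conclusion assumes only that the heading means what it says about the Run-in. It is worth correcting because it concerns eligibility and the handling of possible toxicity, where sites need one answer.

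**What to change.** The sponsor's clinical team should reconcile the screen-failure list, the table heading and the 15 mg tolerance passages (Synopsis, Sections 9.1, 9.3.1 and 9.3.4.3, and footnote 2 of the Schedule of Assessments). The revised text should:

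- give each Run-in finding one stated outcome, including AST/ALT >1.5 x ULN with normal albumin and item f events;
- state, for each table row, which period it governs;
- say whether a reduction or pause in the Run-in counts as not tolerating 15 mg.

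This review does not say which outcome, dose or threshold is right. The cost is a wording clarification by amendment, centred on one section, with no added procedures, visits or subjects.
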